10.0 Study Design / Methods

ARMS 1, 2, and 3: Once a participant has consented and been enrolled they will be randomized by computer (stratified by gender) to one of three treatment groups and the PI and/or their designee will set up a home visit appointment to meet with the participant to obtain baseline data (Table 1). Part of the baseline screening includes the PROMIS Emotional Distress-Depression Short Form 8a. If a participant scores in the severe depression category (raw score 33 and above) a referral will be placed to a mental health professional. Additionally, participants that score in the moderate depression category (raw score 23 to 32) further screening for suicidal ideation will take place. If the participant would admit to suicidal ideation at any time during the study, an emergent mental health consult will be placed through the Charleston/Dorchester Mental Health Center Assessment/Mobile Crisis.

The participant will then be trained on the use of the tablet including the application that will record and transmit their self-entered pain and fatigue symptom scores, the vital sign measuring equipment as well as the video platform for the nurse and self-management program to which they are randomly assigned. The vital sign recording equipment have all been FDA approved and gone through multiple rounds of formal verification. These are also Medical University of South Carolina (MUSC) and South Carolina (SC) Telehealth recommended devices as MUSC is arm of SC Telehealth Alliance. The tablet will be an iPad air 2, which has the communication protocol to connect to all these devices and send encrypted data securely back to servers. In addition, the participants will be given and receive training on a Garmin Vivofit wearable activity tracker that is able to record, steps taken per day, heart rate, distance walked, stairs climbed, and sleep. Garmin Vivofit wearable fitness trackers meet high reliability and validity requirements for parameters such as step counts (Simunek et al., 2016). The training will be conducted via a prerecorded video shown to participants on their tablet at the initial meeting that also explains the program rationale, use of the tablet, activity tracker, and video and app platforms. This video will allow participants access to training at all times in case of issues or questions surrounding the equipment. The PI will contact the participant via their tablet on a weekly basis via the HIPAA compliant telehealth platform Vidyo. Vidyo, a real-time software video communication tool, is HIPAA Compliant with all of the media, signaling, and user login being encrypted to ensure patient privacy and compliance (Vidyo, 2014).²⁸ Each tablet will contain the app "Activate for Life". This app will allow the participant to transmit, via Bluetooth technology their blood pressure and pulse. The app also allows the participant to rate their pain and fatigue scores on a 1-10 scale, document their daily activity and their use of pain medication, and has the ability for the participants to record a voice diary of their daily progress or thoughts. Each participant will receive a blood pressure cuff and will take their blood pressure prior to participating in their PA for the day. The blood pressure and pulse information from the blood pressure monitor will be transferred via Bluetooth to the Activate For Life app on the participants iPad. Once the app has received the data, it will automatically upload the information to the server at MUSC and will be available to be reviewed by the research team. The app will also allow for the participants to input their pain and fatigue scores which will be utilized to monitor pain scores on a daily basis. The vital signs and pain scores will allow for individualizing of the physical activity program to increase or decrease activity based on worsening, improving, or stability of participant's pain as measured by the pain score or through prolonged elevations in blood pressure or pulse. Weekly telehealth visits will allow for delivery of each conditions intervention components, review of pain and/or fatigue, VS, and sleep data. These data will be assessed by the PI and discussed during the weekly telehealth visits with the participants. The burden of self-monitoring and data entry will be captured during feasibility assessments. Saliva samples will be collected from all groups at the beginning and end of the sessions on week 1 and 12 to measure salivary biomarkers including cortisol, and 1,5-AG. Feasibility

Otago. Once a participant has been enrolled and oriented to their tablet, a certified physical therapist (PT) will contact the participant to set up an in-person appointment for initial assessment. During the initial assessment, the nurse PI will conduct the physical assessment screening tests as noted in Table 2. The nurse will then discuss the Otago exercise program with the participant and provide a printed binder of the Otago exercise as well as demonstration on how to appropriately conduct each exercise. The Otago exercise program consists of the following: 1) A series of

Table 1: Prescription of Exercises	
Strengthening	Balance Retraining

The Otago exercise program focuses on major lower limb muscles
 
 ▪ Knee flexors, knee extensors, and hip abductors, which are important for function and mobility ▪ Ankle dorsiflexor and plantar flexor muscles, which are important for maintaining balance. 
Determine the starting level of each exercise by the amount of ankle weight the patient can lift to perform eight to ten good quality repetitions before fatigue. This must be assessed for each muscle group on each leg.
 
Recommend that patients aged 80 and older start with two to four poundweights.
 
Starting with light weights at the outset will minimize both muscle soreness and compliance problems.
 
Ensure throughout prescription that:
 
 ▪ The patient uses adjustable ankle weights. ▪ There is minimal substitution of other muscle groups. ▪ The participant uses the correct breathing technique (inhale before a lift, exhale during, and inhale while lowering the lift). ▪ The participant does the exercises slowly (two to three seconds to lift the weight, four to five seconds to lower the weight) through the functional range of active joint movement. ▪ The participant takes a one to two minute rest between sets. 	
 ▪ Observe the participant during the holding portion of each balance exercise. Make sure they can recover their balance using lower body strategies (as opposed to grabbing with their arms) before prescribing the exercise without support. ▪ Not everyone will start at the first level or be prescribed all of the balance exercises. Unstable patients may initially need a wider base of support. ▪ Ensure the patient's eyes stay looking ahead ▪ It is okay to make lower limb balance adjustments, such as taking a recovery step, while doing the exercise and is confident in doing so.

warm-up exercises, 2) Select exercises from the 17 Otago exercises which challenge the participant's strength and balance for up to 30 minutes, three times a week, 3) A walking program for up to 30 minutes, three times a week. Each Otago will be tailored for each participant's ability level. See exercise prescription in Table 1.

3C3.B. Otago + GYYB + (GYJB): The GYYB program will be administered to the participants by a qualified and certified Yoga instructor in a group setting once a week for 12 weeks. The GYYB is a one-hour program containing gentle physical Yoga postures that participants could practice sitting on a chair for 30 minutes. These exercises are designed based on improving the overall flexibility, bodily control and mindfulness in movements. Following the gentle yoga postures, the participants will perform Yogic breathing exercises for 30 minutes. These exercises are known to promote relaxation, mood, pain and anxiety scores that are highly relevant to the target population and are reported to stimulate measurable biomarker changes in the saliva. During the in-person session the Yoga instructor will explain the GYYB program to participants in the Otago+GYJB group each exercise and their perceived benefits. The participants will have a chance to practice the exercises in the presence of the instructor and clarify any question that they might have about the exercises. The instructor will make sure that the participants can perform the exercises independently. The participants will be provided with a video and a handout for the study exercises that they will follow for 1 hour every day (any time at their preference). Any deviations in the practice will be noted by the participants in a diary indicating the length of the practice with date on it. Saliva samples will be collected at the beginning and end of the sessions on week 1 and 12 to measure salivary biomarkers including cortisol, and 1,5-AG. The OEP and self-management as detailed above will also take place in this group.

3C3.C. Otago plus GYYB + Behavior Activation (*Activate for Life*).

This condition will incorporate OEP and GYYB as above and will also include behavioral activation to address motivation and affect. Behavioral Activation incorporates daily planners and worksheets to identify and rate reinforcing behaviors and is often used in conjunction with other interventions because components of these interventions are easily incorporated into the daily planner based activities. Each participant outlines general values and specific behaviors that 'demonstrate' each value, compiling a list of the latter. This list is then used to generate 10 to 20 highly defined values-based, reinforcing activities. Next, this list is combined with the activities outlines in Otago and GYYB and this master list is used to schedule these values-based activities for the next two days. One of the strengths of the BA protocol, relative to other cognitive behavioral and activation-based interventions, is that it is designed for implementation over a brief period. Additionally, sessions of the often require as few as 15-30 minutes of contact time due to the straightforward, simple structure of these sessions. Patients begin with a weekly self-monitoring exercise, charting behaviors and mood every hour, that serves as a baseline assessment of daily activities, and orients the patient to the quality and quantity of his or her activities on a daily basis. Also, baseline assessment assists in generating ideas about activities to target during treatment.

Session 1: Begins with rationales for Behavioral Activation. The core points made are that what one does often plays a role in how one feels. Clients then proceed to identify 5 classes of values (e.g., family, work, spirituality) with specific behaviors that 'show' the patient's value, thus the treatment is tailored for each individual. For example, the value 'time with family' might be shown by 'throwing the baseball with son for 20 minutes'. Lists of specific behaviors are derived for each value and written on the daily planner. Participants are then given a daily planning calendar and behaviors that are reinforcing and relatively easily accomplished are planned each day, for two days in advance with the objective of planning at least 2 hours of reinforcing activities and scheduled homework from Otago and GYYB each day. Session 2: Begins with a review of homework and verbal reinforcement of completed planners, completed reinforcing behaviors, completed Otago and GYYB homework,

restatement of the rationale (ie., that what one does affects how one feels and doing positive things will help one to feel positively), and problem solving. Behaviors that were consistently planned but not completed are removed and alternative behaviors suggested. The next 2 days' activities are planned. This session usually involves a significant amount of problem solving, and identification of avoidance, with planning in place to counter this avoidance. Sessions 3-4: These sessions begin with a review of homework, followed by asking the patient to state, in their own words, their interpretation of the rationale for Behavioral Activation. Obstacles to completing behaviors are discussed and additional exposure-based and reinforcing behaviors are generated. The next 2 day's activities are planned. Session 5: Includes discussion of the rationale and treatment gains obtained thus far. Discussion is also centered on the need to continue planning activities and using a daily planner for at least 6 months. Relapse prevention strategies are reviewed. Additional sessions are conducted every other week until week 12 (Otago and GYYB completion).

Table 2: Measurements/Instruments/Interventions and Time Points		
Major tasks and domains; monitor/ evaluate	Measures/instruments/questions and Cronbach's alpha ()	Data sources and time points
Screening	Ability to ambulate 150 feet with or without assistive device; Short version of Test for Functional Health Literacy in Adults (0.97) ³⁷ Tablet Computer Familiarity Questionnaire (0.92) ³⁸ Mini-Cog ²⁶	Participant interview and observation; Baseline
Demographics	Personal health, medical, health history—co-morbidities, medications, use of pain medications, race/ethnicity	Participant interview; Baseline
Weekly nursing self-management	Review weekly diary entries, pain scores, yoga and /or Otago progress, fatigue, and sleep.	Weekly
Reach: Sample Recruitment	Progress monitoring of sample representativeness; types of recruitment activities and rates; % eligible, consented, oriented	Tracking forms; weekly quality checks by PI; weekly team meetings
Effectiveness: Functional impacts Pain	Numerical rating scale NRS (0.99) ³⁹ PROMIS Pain Interference Short Form 6b (0.98) ⁴⁰ PROMIS Pain Behavior Short Form 7a (0.98) ⁴⁰ PROMIS Fatigue Short Form 6a (0.91) ⁴¹	Baseline; Daily; Study end Baseline; Study end Baseline; Study end Baseline; Daily; Study end
Fatigue Lower extremity strength Balance and Function Walking capacity	30 Second Chair Stand Test (not determined) ⁴² Mini Balance Evaluation Systems Test (MiniBEST) (0.91) ⁴³ Two Minute Walk Test (0.82) ⁴⁴	Baseline; Study end Baseline; Study end Baseline; Study end
Self-report measures Function Depression Social support Self-efficacy	PROMIS Physical Function (0.95) ⁴⁵ PROMIS Depression Short Form 8a (0.95) ⁴⁶ Revised UCLA Loneliness Scale (0.94) ⁴⁷ Pain Self-Efficacy Scale (0.93) ⁴⁸	Baseline; Study end Baseline; Study end Baseline; Study end Baseline; Study end
Adoption Adherence	Participation in weekly self-management telehealth visits; frequency of participation in Otago and/or Yoga as recorded in participant diary and data from activity tracker; frequency of use of self-management techniques as recorded in participant diary; # of patients who successfully complete self-management program; # of and reasons for dropouts	Tracking forms; weekly review of participant diary; weekly assessment of feedback; end of study participant interviews and satisfaction questionnaires
Acceptability		

Endorsement	Usability of tablet technology and activity tracker; # and types of problems encountered; participant satisfaction with self-management program and technology	Assess at weekly team meetings; acceptability checklist and tracking forms; end of study participant interviews and satisfaction questionnaires
Implementation		
Technology	# of problems encountered with tablet, activity tracker, vital sign equipment; # and types of problems encountered with study setup; was fidelity to training protocol maintained; was orientation completed as planned; was standardized checklist used to instruct participants; assessment of participant for suggestions; # of changes made to intervention based on suggestions	Tracking forms; weekly team meetings; end of study participant interviews and satisfaction questionnaires
Site set up		
Consistency of intervention		
Maintenance		
Projection of future adoption	# patients who would continue intervention; potential for future applications	End of study participant interviews and satisfaction questionnaires

End of Study Interviews: At the end of Visit 2, participants under ARMS 1, 2, and 3 are scheduled an end of study phone exit-interview with [name] at University NC Charlotte (UNCC). This interview will be recorded and temporarily stored on a digital voice recorder while the participant is on speaker phone. Prior to the beginning of the recording, [name] will inform the participant that the recording is about to commence and at the end of the interview he will notify them that the recording has ceased. In this manner, no PHI will be collected. Prior to performing qualitative analysis, [name] will immediately upload the recording to the patient's electronic case record in the REDCap database on MUSC secure servers and the delete the recording from the portable storage device.

Supplemental ARM 4 Study Design:

Participants enrolled under this study arm will solely receive the gentle yoga and yoga breathing 12-week (GYBY) component exercise program which will be loaded on to a tablet that will given to the participant while enrolled in the study. There are only two study visits (baseline and week 12) with no 3 month follow-up, at which timepoints saliva samples will be collected.

CG measures to be collected under the Supplemental ARM at the two timepoints include:

- Demographics. Age, race/ethnicity, sex, marital status, socioeconomic status, education, living arrangement, medications, # co-morbid conditions (health status) will be recorded.
- PROMIS v1.0/1.1 Short Forms (intraclass correlation coefficient)
- Health status: Global Health Scale (0.81)
- Functional health: Physical Function (0.95)
- Fatigue: Fatigue 6a (0.91)
- Sleep disturbance: Sleep Disturbance 6a
- Depression: Depression 8a (0.95) and CES-D (0.90)
- Anxiety: Anxiety 6a (0.94)
- Loneliness: UCLA Loneliness Scale (0.96)
- Social support: Medical Outcomes Study Social Support Survey Instrument (MOS-SS) (0.97)
- Burden: Zarit Burden Scale (0.89)
- Relationship quality (CG): Mutuality Scale (0.94)
- QoL (CG): Euroqol-5D (0.83)
- QoL (PWD): Quality of Life-Alzheimer's Disease (0.82)
- Function (PWD): Functional Assessment Staging Tool (0.87)
- Activities of Daily Living Questionnaire (dementia) (0.86)
- International Physical Activity Questionnaire for the Elderly (IPAQ-Short Form)

- End of study satisfaction survey (researcher developed)

The participant sample will be characterized using univariate descriptive statistics and frequency distributions for all variables as appropriate. We will also explore differences in demographic and other variables such as age (45-74, ≥ 75 years), sex, health status, functional activity, and QoL across the 2 time points.

Participant Compensation: Participants under ARMS 1, 2, and 3 will receive \$20 for screening, and \$20 at the initial enrollment visit for completion of the initial enrollment assessment and baseline surveys (total of \$40 if eligible and enrolled). Additionally, participants will receive another \$40 at successful completion of the post-treatment (week 12) and 3 month followup visits. Total compensation for successful study completion is \$120.00. All payments will be made to the participant in the form of a gift card.

Participants under the Supplemental ARM 4 will be provided a total amount of \$80 in study compensation \$40 for enrollment and completion of the baseline visit, and \$40 at successful completion of study at visit 2. Payment will be made in the form of a check that will be mailed to the participant's home address. Will collect social security numbers for MUSC IRS tax reporting purposes.

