18.0 Drugs or Devices

This study does not involve the use or storage of any drug product. All investigational supplies and materials are readily commercially available and are not industry regulated. All study supplies (tablets) will be inventoried and stored in a locked cabinet, behind a locked door by the researchers. Study supplies will be dispensed individually to each participants after enrollment and group assignment.

A&D Medical Premium Wireless Blood Pressure Monitor is an FDA approved, Bluetooth blood pressure cuff that will be utilized to collect participants blood pressure and pulse and transmit the data to the "Activate for Life" application.

The "Activate for Life" app is an application that will be available on participants tablets. This app has the ability to receive Bluetooth data from the A&D wireless blood pressure monitor. The app will also allow participants to enter their pain and fatigue levels on a "1-10" scale, ask participants to input their PA and their use of pain medication for the day, and record thoughts on a voice recorded daily diary. This information will transmit from the application to a firewall protected server at MUSC where it will be available to the research team. No medical information will be stored on the app.

References:

2. Laubenstein, S., & Beissner, K. (2016). Exercise and Movement-based Therapies in Geriatric Pain Management. *Clinical Geriatric Medicine*, 32, 737–762. <http://dx.doi.org/10.1016/j.cger.2016.06.002>
3. Liu, C.J. & Latham, N.K. (2009). Progressive resistance strength training for improving physical function in older adults. *Cochrane Database Systematic Review*, 8(3), CD002759. doi:10.1002/14651858.CD002759.pub2.

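### Arms 1–3: as written, randomisation comes before the baseline home visit, and nothing withholds the arm until baseline is recorded; the physical tests are the most exposed

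*Protocol*

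**What the plan says.** For Arms 1, 2 and 3, Section 10.0 of the Protocol gives the order of events in one sentence. It begins "Once a participant has consented and been enrolled they will be randomized by computer (stratified by gender) to one of three treatment groups". It then has the PI or a designee "set up a home visit appointment to meet with the participant to obtain baseline data", citing Table 1.

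The next steps are these:

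- **Training.** "The participant will then be trained on the use of the tablet", and the training extends to the "self-management program to which they are randomly assigned". On delivery: "The training will be conducted via a prerecorded video shown to participants on their tablet at the initial meeting". The same video explains the rationale of the programme.
- **Supplies.** Section 18.0, whose study supplies are the tablets, states: "Study supplies will be dispensed individually to each participants after enrollment and group assignment".
- **Physical assessment.** The Otago paragraph of Section 10.0 opens with "Once a participant has been enrolled and oriented to their tablet". A physical therapist then arranges an in-person appointment, at which "the nurse PI will conduct the physical assessment screening tests as noted in Table 2".

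Sections 3C3.B and 3C3.C carry the Otago component into the other two arms, so this sequence applies to every randomised participant.

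The only mention of unblinding is in Section 11.0 and concerns the saliva analysis. The SAP says nothing on when baseline is taken relative to allocation.

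**The concern.** Baseline does real work in this trial. It is one of the three time points of the treatment-by-time design in Section 3.0, and so enters the SAP's repeated measures ANOVA across the three arms. It is also the reference for the within-subject hypothesis of Aim 3. If a participant who knows the arm tries harder or less hard on an effort-dependent test, or the assessor scores differently, and this happens in some arms but not others, the difference enters the between-arm comparison as if it were an effect. The pilot is meant to supply an efficacy signal and power inputs for a full-scale RCT, so both the distortion and the visit order could be carried forward.

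The plan describes no independent baseline assessor: the PI who runs the physical tests also has weekly contact with participants.

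**Working it through.** **Order of events, outcome by outcome**

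1. *Physical tests.* Section 18.0 dispenses tablets after group assignment, tablet training covers the assigned programme, and the Otago paragraph places the assessment after tablet orientation. These three statements put that assessment after allocation without relying on the word order of the randomisation sentence. Which tests are meant is unclear. The Screening row of Table 2 holds the 150-foot walk and the Mini-Cog, while the chair stand, MiniBEST and two-minute walk are in other rows. The first two look like eligibility items, so the last three are the more natural reading.
2. *Fatigue, depression and other self-report forms.* They follow randomisation, but the word then in the training sentence suggests that they come before programme training. Disclosure before them is possible but not shown.
3. *Pain.* At least one PROMIS pain score decides eligibility (Section 5.0), and eligibility is verified before enrolment (Section 13.0, Arms 1–3 plan, Section B). No text says whether that score or a later one is the analysis baseline.
4. *Saliva.* Sampling is tied to the start and end of a week-1 session, so it follows allocation by design.
5. *Other signals.* Participant Compensation in Section 10.0 links the baseline surveys to an initial enrolment visit, which may imply another order. Section 10.0 cites Table 1 for baseline data, but Table 1 is the exercise prescription; Table 2 appears intended.

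**Illustration of size**

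The documents give no figure to reproduce. From the documents: G = 3 arms, n = 10 per arm, α = 0.05, and T = 2 time points for the physical tests (Table 2). Assumed: no true effect, compound symmetry with correlation ρ = 0.6, and a baseline-only shift of s SD in one arm, or the same shift in two arms. The sum of squared deviations of the three arm shifts from their mean is then SS = (2/3)s².

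*Arm-by-time test:* noncentrality = n·SS·(1 − 1/T)/(1 − ρ) = 10·(2/3)s²·0.5/0.4 = 8.33s², on (G−1)(T−1) = 2 and G(n−1)(T−1) = 27 df.

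*Arm main effect:* the shift in each participant's mean is s/T and the variance of that mean is [1 + (T−1)ρ]/T. Noncentrality = n·SS/{T[1 + (T−1)ρ]} = 10·(2/3)s²/(2·1.6) = 2.08s², on 2 and 27 df.

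| Shift s (SD) | Noncentrality, arm-by-time | False-positive rate | Noncentrality, main effect | False-positive rate |
|---|---|---|---|---|
| 0.1 | 0.083 | 5.6% | 0.021 | 5.1% |
| 0.2 | 0.333 | 7.3% | 0.083 | 5.6% |
| 0.3 | 0.750 | 10.4% | 0.188 | 6.3% |

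*Sensitivity, arm-by-time test.* With s = 0.2 and ρ from 0.4 to 0.8, the rate runs from 6.5% to 9.8%. With three time points and ρ = 0.6, the three rates are 5.5%, 7.1% and about 10%. If all three arms shift equally, SS = 0 and the rate stays at 5.0%.

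*Could a baseline table reveal such a shift?* The standard error of a difference between two arms is √(2/10) = 0.447 SD. With t(18) = 2.101 the 95% confidence interval is about ±0.94 SD, far wider than the shifts considered.

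**The case against.** The strongest reply is that the mechanism is weak where the order is clearest. Otago, the strength and balance component, is in all three arms, so expectations about the physical tests arise largely in every arm, and a common shift does no harm to the arm-by-time test. The Otago paragraph also has the nurse discuss Otago after the tests, and detailed teaching of yoga and Behavioral Activation comes later still. If the chair stand, MiniBEST and two-minute walk are actually done at the home visit, they precede programme training, though they still follow randomisation. All of this stands, and it limits the likely size of the problem. It does not supply the missing safeguard, because tablet training has already covered the assigned programme by the time the nurse PI's assessment is arranged.

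It is also fair to say that the feasibility measures of Aim 2 do not depend on baseline scores, and that the SAP, written in the past tense, describes analyses already done.

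A reader might go further and infer that the baselines for the Aim 3 outcomes (pain, fatigue and depression) were given in knowledge of the arm, or that the trial's comparisons are biased. The documents do not support either inference. A pain score precedes enrolment, the forms appear to precede training, and no document gives a shift, its direction or a correlation.

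**Conclusion.** The concern holds in a limited form. As written, randomisation precedes the baseline home visit, the nurse PI's physical assessment follows group assignment and tablet orientation, and nothing withholds the arm until baseline is recorded. That exposes baseline to arm knowledge; it does not show that any value was affected. What happened in practice cannot be seen from the documents.

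The percentages above rest wholly on assumed shifts and an assumed correlation. They also depend on the term tested: the SAP refers to differences between the arms without naming the arm-by-time interaction, and the main effect is much less sensitive. Severity is minor; the value of the point is that it is cheap to put right. Arm 4 is not randomised and is unaffected.

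**What to change.** Reorder Section 10.0 for Arms 1–3: consent; eligibility; all Table 2 self-report and physical baseline measures completed and saved; then generation or release of the allocation; then tablet and programme training. In addition:

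- Reconcile the randomisation paragraph, the Otago paragraph and Participant Compensation, and correct the reference to Table 1.
- State which tests the Otago paragraph means.
- Name the PROMIS pain score, from screening or from the home visit, that serves as the analysis baseline.
- Leave the saliva sampling as designed, and note that its baseline follows allocation.
- For participants already enrolled, report for each outcome whether baseline preceded disclosure of the arm. The new order then serves any further enrolment and the full-scale RCT.

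The cost is mainly wording. Because the physical assessment is a separately arranged appointment, either the home visit becomes longer or the allocation and training wait for that appointment, and staff need materials ready for any arm. Later visits stay open to arm knowledge, so the change removes only the baseline part of the risk.
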